## **1.6 Hypothesis**

We hypothesize that the combination of ADT and radium-223 dichloride will increase the depth of PSA response and will target bone metastases effectively in subjects with newly diagnosed prostate cancer and skeletal metastases, reflected in a higher percentage of subjects achieving a PSA value of 0.2 ng/mL or less ("undetectable PSA") after 7 months of combination therapy compared to ADT alone and a greater proportion of subjects normalizing an elevated serum total alkaline phosphatase level after 12 weeks of combination therapy compared to ADT alone. We will use the primary endpoint of 12-month radiologic progression free survival (rPFS). We hypothesize that if the trial meets the primary endpoint, radium-223 dichloride would be worthy of future testing in phase 3 trials.

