### **2.2 Secondary Objectives**

2.2.1 Assess safety and toxicity including incidence of skeletal related events (SRE) and secondary neoplasms.

2.2.2 Estimate the proportion of subjects with  $PSA \leq 0.2$  ng/mL after 7 months of androgen deprivation therapy, the proportion of subjects with  $PSA \leq 4$  ng/mL after 7 months of androgen deprivation therapy, the median time to castration resistance, 2-year PSA progression free survival proportion (PCWG2 criteria) and 2-year overall survival proportion in both arms.

2.2.3 Determine the proportion of subjects with elevated serum total alkaline phosphatase (ALP) at baseline who normalize their alkaline phosphatase after 12 weeks of therapy, assess time to ALP progression ( $\geq 25\%$  increase in ALP from baseline/nadir (whichever is lower) and above ULN), association of ALP x in both arms.

2.2.4 Evaluate change in pain level and analgesic use using the Brief Pain Inventory (BPI short form) and WHO ladder scale, respectively, with therapy.

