## 12.4 Analysis Datasets

### Methods of Statistical Analysis

The definitions of the study populations are listed below.

Population	Definition
Enrolled	This will comprise all subjects who meet the eligibility criteria and are registered onto the study.
Evaluable	This will comprise all subjects who receive at least one dose of trial drug and either undergo at least one post-baseline assessment or die before any evaluation.
Intention-to-treat (ITT)	This will comprise all subjects who meet the eligibility criteria and are registered onto the study irrespective of their compliance to the planned course of treatment. (See Intent-To-Treat principle below).

Population	Definition
Per Protocol Set	This will comprise all subjects who received ADT or ADT+R for 1 cycle and have a radiographic assessment post-baseline.
Safety	All subjects who receive 1 dose of treatment will be included in the safety population.
Treated	This will comprise all subjects who have been exposed to the planned course of treatment to any extent.
ALP normalization	Subjects with abnormal ALP at baseline and at least one other post-baseline ALP measure.

Intention-To-Treat Principle - The principle that asserts that the effect of a treatment policy can be best assessed by evaluating on the basis of the intention to treat a subject (i.e. the planned treatment regimen) rather than the actual treatment given. It has the consequence that subjects allocated to a treatment group should be followed up, assessed and analyzed as members of that group irrespective of their compliance to the planned course of treatment.

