### 12.7 Analysis of Secondary Objectives

Toxicity will be described within each arm by type, maximum grade and frequency among the safety population. The proportion of subjects in each arm with skeletal related events and secondary neoplasms will be reported individually and a mid p-value test will compare the proportions between arms.

Time to castration resistance (TTCR), PSA progression free survival (PCWG2 criteria), and Overall Survival (OS) will be reported by arm using Kaplan-Meier methods and tested using the log-rank test. The –time to castration resistance, the 2-year PSA PFS and OS proportions with 90% confidence intervals will be reported using Kaplan-Meier methods. Analyses will be completed on the ITT population.

Binomial proportions with 90% binomial confidence intervals of subjects who achieve PSA  $\leq$  0.2 ng/mL at 7 months after treatment initiation will be reported by arm. Similarly, the proportions and associated confidence intervals of subjects who achieve PSA  $\leq$  4 ng/mL at 7 months after treatment initiation will be described.

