We will evaluate the distribution of pre-randomization marker levels (ALP and bone markers) among those who have and have not started ADT prior to randomization. If it appears that the prior initiation of ADT impacts the study entry bone marker levels to a fair extent, then all marker analyses will be conducted stratified by ADT initiation status. Descriptive statistics by arm will report the time to ALP progression among all subjects using Kaplan-Meier methods. ALP and serum bone markers will be reported by arm for each time-point using means or medians and corresponding measures of variability for all subjects with serum. Percentage change in ALP from baseline and changes from baseline in bone markers will be calculated for each later time point and tested between arms using a t-test or Wilcoxon rank test. If there is sufficient data, a mixed model will be used to model each endpoint over time to determine if the changes are different between treatment arms. Exploratory analysis will use separate Cox models with rPFS, PSA PFS, TTCR, and OS as the individual outcomes and treatment group, one marker, and the interaction between treatment and marker as independent covariates to find associations with outcomes. These models can be expanded to include other subject factors to determine if the marker contributes to outcome above subject factors that are known to be associated with the outcome. Similarly, logistic models can be used with 7-month PSA outcomes. The model analyses are considered exploratory for this trial. Thus, they are not powered and will not use multiple comparisons adjustments.

Worst pain will be reported from the BPI (SF) at each time point with a mean or median and the associated measure of variability and tested between arms with a t-test or Wilcoxon rank test. Comparisons at the times post-baseline will be compared between treatment arms using a paired test (t-test or Wilcoxon rank test.) WHO will be reported categorically by arm at each time point and tested between arms using the Mantel-Haenszel chi-square test. The change in WHO score from baseline will be calculated and be the outcome in a cumulative logistic model. Treatment arm will be included as an independent covariate to test if the change in pain is different between arms. Each post-baseline measure will be a separate model.

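### Section 12.7 commits to no between-arm comparison of 7-month PSA ≤ 0.2 ng/mL or 12-week ALP normalization, although section 1.6 hypothesizes that radium improves both

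*Combined protocol and SAP*

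**What the plan says.** **Hypothesis.** Section 1.6 makes two comparative statements about binary outcomes. One is that the combination's effect will be "reflected in a higher percentage of subjects achieving a PSA value of 0.2 ng/mL or less" after 7 months. The other is that there will be "a greater proportion of subjects normalizing an elevated serum total alkaline phosphatase level after 12 weeks of combination therapy compared to ADT alone".

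**PSA objective and analysis.** Objective 2.2.2 is worded as estimation: "Estimate the proportion of subjects with" PSA at or below 0.2 and 4 ng/mL, in both arms. Section 12.7, like the synopsis, plans "Binomial proportions with 90% binomial confidence intervals of subjects who achieve PSA" ≤ 0.2 at 7 months, reported by arm, and the same for ≤ 4. It gives no difference, ratio, interval for a contrast, or test. Further on, among the exploratory marker models, it adds: "Similarly, logistic models can be used with 7-month PSA outcomes".

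**ALP normalization.** This is a secondary objective (2.2.3), a listed outcome measure (synopsis) and a defined endpoint (8.11). Section 12.4 gives it its own population: "Subjects with abnormal ALP at baseline and at least one other post-baseline ALP measure". Section 12.7 attaches no analysis to it. For ALP, 12.7 covers time to ALP progression descriptively, and: "Percentage change in ALP from baseline and changes from baseline in bone markers will be calculated for each later time point and tested between arms".

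**Other secondary endpoints.** For skeletal related events and secondary neoplasms, "a mid p-value test will compare the proportions between arms". Time to castration resistance (TTCR), PSA progression-free survival, overall survival, bone markers, worst pain and WHO score are also tested between arms.

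**The concern.** The two proportions that section 1.6 singles out are the ones for which section 12.7 commits to no comparison. Estimation wording does not explain this. TTCR, PSA progression-free survival and overall survival sit in the same objective 2.2.2, under the same verb, and 12.7 tests all three.

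What is at stake is how well the trial can speak to its own hypothesis. For PSA, the only committed output is two separate intervals, which are a poor basis for judging a difference. For ALP normalization there is no committed output. In both cases the contrast, stratification, denominator and handling of missing values would be chosen after the data are known, which a prespecified plan should prevent.

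**Working it through.** **1. The plan's own figure.** No sample size or power is stated for either proportion. The only stated design figure is for rPFS: 140 events, one-sided alpha 0.10, 90% power, 1:2 allocation, medians 12 and 19 months (12.1). By Schoenfeld's formula:

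(1.2816 + 1.2816)² / [(1/3)(2/3)(ln(12/19))²] = 6.57 / (0.2222 × 0.2112) = 140.

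This reproduces and is not in question.

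**2. Inputs for the PSA illustration.**
- Arm sizes 68 and 136 (12.1).
- 90% intervals (12.7), so z = 1.645.
- A 45% rate of PSA ≤ 0.2 at month 7. Section 1.1 reports this for a previous ADT trial; for the present trial it is an assumption.
- The same rate in both arms and no missing 7-month values, also assumptions.

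**3. Half-widths.**
- ADT arm: 1.645 × √(0.45 × 0.55/68) = 0.099.
- ADT + radium arm: 1.645 × √(0.45 × 0.55/136) = 0.070.
- Gap needed for the two intervals to separate: 0.099 + 0.070 = 0.169.
- Half-width of a 90% interval for the difference: 1.645 × √[0.45 × 0.55 × (1/68 + 1/136)] = 0.122.

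The ratio is 0.169/0.122 = 1.39. With a common rate and 1:2 allocation it equals (1 + 1/√2)/√(1 + 1/2) = 1.39 whatever the rate. The widths in points do depend on the rate. At 30%, √(0.30 × 0.70/n) gives 0.091 + 0.065 = 0.156 against 0.112. At 60%, √(0.60 × 0.40/n) gives 0.098 + 0.069 = 0.167 against 0.120.

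**4. Probability of seeing a real difference in PSA ≤ 0.2 (68 v 136, control 45% assumed).** The direct comparisons use the normal approximation. Non-overlap is by exact enumeration, with Clopper-Pearson intervals for the lower figure and Wald intervals for the upper.

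| Rates | Direct, one-sided 0.05 (as a 90% interval for the difference) | Direct, one-sided 0.10 | Non-overlap of per-arm 90% intervals |
|---|---|---|---|
| 45% v 55% | 0.38 | 0.53 | 0.14–0.19 |
| 45% v 60% | 0.65 | 0.77 | 0.34–0.42 |
| 45% v 65% | 0.86 | 0.93 | 0.61–0.68 |
| 45% v 70% | 0.97 | 0.99 | 0.84–0.88 |

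With equal rates, non-overlap in favor of radium occurs with probability only about 0.007–0.013.

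**5. ALP normalization.** The documents give neither the share of subjects with abnormal ALP nor any normalization rate. Assume 40–60% abnormal (27 v 54 to 41 v 82 subjects), control rates of 30–50% and a 20-point difference. A direct one-sided 0.10 comparison then has power of about 0.67–0.81, so the comparison would be informative if it were planned.

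**6. Stratification of the ALP comparison.** Baseline ALP, normal v abnormal, is one of the two randomization factors (4.1). The normalization set holds only subjects with abnormal baseline ALP, so that factor cannot usefully stratify it. Extent of disease can.

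**7. Denominators.** The population in 12.4 asks for any post-baseline ALP value, whereas the endpoint is at 12 weeks. The ITT statement in 12.7 stands with the time-to-event endpoints and is not repeated for the PSA proportions.

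**The case against.** The PSA analysis does what objective 2.2.2 asks, since that objective says "Estimate the proportion of subjects with" the PSA levels concerned. Section 1.6 is a rationale, and it rests the case for phase 3 testing on the primary endpoint. Rewording 1.6 as estimation would also remove the PSA mismatch. This has weight, but it leaves ALP normalization without an analysis and does not explain why other endpoints in 2.2.2 are tested.

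The plan is also not silent on comparison. Logistic models may be fitted to 7-month PSA, and percentage change in ALP is tested between arms. Both facts narrow the point without closing it. The logistic models are optional and exploratory, and follow the pattern of treatment, one marker and their interaction; in such a model the treatment term is conditional on the marker value. A test of percentage change bears on ALP response but does not compare the proportions that normalize.

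A reader might infer that the plan will judge the PSA hypothesis by whether the intervals overlap, and so imposes the loss of power in the last column of the table. The documents do not support that. No overlap rule is stated, and anyone with the per-arm counts can compute an unadjusted difference. The figures show only what is lost if the committed output is read that way.

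**Conclusion.** The point holds as a gap in the secondary analyses. Two comparative claims in section 1.6 have no committed between-arm analysis in section 12.7, and one of them, ALP normalization, has no analysis there despite its own population.

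For PSA ≤ 0.2, a 90% interval for the difference has a half-width of about 12 points, against a gap of about 17 points before the per-arm intervals separate. This assumes a 45% rate in both arms, all 68 and 136 subjects, and no missing values. The ratio of 1.39 does not depend on the assumed rate, but the points do. The ALP power figures rest wholly on assumed rates.

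It would go too far to say that the hypothesis cannot be answered, since the counts allow an informal comparison. The primary rPFS test and its sample size are untouched. This is a cheap improvement, not a flaw in the main design.

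**What to change.** In section 12.7, and in the matching synopsis text:

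- **PSA ≤ 0.2 and PSA ≤ 4.** Keep the per-arm 90% intervals. Add the difference in proportions (ADT + radium minus ADT) with a 90% interval, by Mantel-Haenszel, stratified by extent of disease and baseline ALP.
- **ALP normalization.** Add per-arm proportions with 90% intervals, and the difference with a 90% interval stratified by extent of disease only.
- **Denominators and missing data.** Name the analysis set for each proportion, and say how a missing 7-month PSA or 12-week ALP value is counted.
- **Status.** Label these comparisons as secondary, without multiplicity control.

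If the sponsor intends estimation only, section 1.6 should say so, and ALP normalization still needs an analysis in 12.7.

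The cost is a few sentences. No extra subjects, visits or samples are needed. The downside is two or three more unadjusted secondary comparisons, which the labelling should make plain.

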## **2. OBJECTIVES**

### **2.1 Primary Objective**

2.1.1 Determine whether the combination of ADT plus radium-223 dichloride is more effective than ADT alone based upon radiologic progression free survival (rPFS) of subjects with newly diagnosed metastatic prostate cancer with bone metastases.

### **2.2 Secondary Objectives**

2.2.1 Assess safety and toxicity including incidence of skeletal related events (SRE) and secondary neoplasms.

2.2.2 Estimate the proportion of subjects with  $PSA \leq 0.2$  ng/mL after 7 months of androgen deprivation therapy, the proportion of subjects with  $PSA \leq 4$  ng/mL after 7 months of androgen deprivation therapy, the median time to castration resistance, 2-year PSA progression free survival proportion (PCWG2 criteria) and 2-year overall survival proportion in both arms.

2.2.3 Determine the proportion of subjects with elevated serum total alkaline phosphatase (ALP) at baseline who normalize their alkaline phosphatase after 12 weeks of therapy, assess time to ALP progression ( $\geq 25\%$  increase in ALP from baseline/nadir (whichever is lower) and above ULN), association of ALP x in both arms.

2.2.4 Evaluate change in pain level and analgesic use using the Brief Pain Inventory (BPI short form) and WHO ladder scale, respectively, with therapy.

## 2.3 Exploratory Correlative Objectives

- 2.3.1 Assess number of circulating tumor cells (CTCs) and gamma H2AX in all subjects (number of subjects = 204).
- 2.3.2 Explore the association of bone turnover markers with clinical outcome and change in serum bone turnover markers with therapy in both arms.

## 3 ELIGIBILITY CRITERIA

### 3.1 Inclusion Criteria

#### Definitions:

- **Androgen Deprivation Therapy** includes LHRH agonist or LHRH antagonist or bilateral orchiectomy. Anti-androgen receptor blockers (e.g. bicalutamide) do not constitute androgen deprivation therapy.
- **Protocol specified therapy** refers to the androgen deprivation therapy (see above) with or without radium-223 dichloride.

1. All subjects or their legally authorized representative must be informed of the investigational nature of the study and provide written informed consent and HIPAA authorization for release of personal health information before performance of any study related procedure not part of routine medical care.  
**NOTE:** HIPAA authorization may be included in the informed consent or obtained separately.
2. Men  $\geq$  18 years of age at the time of informed consent.
3. Histological or cytological evidence of prostate adenocarcinoma.
4. All subjects must have radiologic or pathologic evidence of skeletal metastases with  $\geq$  2 skeletal lesions with or without pain at baseline on bone scan or axial imaging or with 1 skeletal lesion and bone pain within 28 days prior to the registration.
5. All subjects must have a radiographic assessment (chest or abdominal/pelvic CT or MRI) within 28 days prior to registration but do not need to have measurable disease.
6. ECOG (Eastern Cooperative Oncology Group) Performance Status of 0-2 within 28 days prior to registration (see Study Procedures Manual [SPM] for ECOG Performance Status definitions). ECOG Performance Status of 3 will only be allowed if judged by the site investigator as attributable exclusively to bone pain.
7. Subjects must fall into one of the two populations below:
  - **Early Induction Group:** Subjects who have started androgen deprivation therapy (luteinizing hormone–releasing hormone (LHRH) agonist or antagonist therapy with or without an antiandrogen agent) a maximum of 28 days before registration and who otherwise meet all the eligibility criteria.
  - **Late Induction Group:** Subjects who have NOT started any androgen deprivation therapy (luteinizing hormone–releasing hormone (LHRH) agonist or antagonist therapy with or without an antiandrogen agent).

8. Anti-androgen receptor antagonist therapy must be bicalutamide. Subjects already started on other anti-androgens must be willing to switch over to bicalutamide.
9. Any prior androgen-deprivation therapy or finasteride as neoadjuvant or adjuvant therapy or for biochemical recurrence must have been discontinued at least 6 months prior to registration.
10. Prior surgical treatment for prostate cancer is allowed but must have been completed at least 14 days prior to registration and any toxicity from such therapy must have recovered to  $\leq$  grade 1 per CTCAE version 4 criteria by the time of registration.
11. The following laboratory values must be obtained within 28 days prior to registration for protocol therapy.
  - Hemoglobin (Hgb)  $\geq$  8.0 g/dL (80 g/L) without packed RBC transfusion
  - Platelets  $\geq$  100 K/mm^3
  - Absolute neutrophil count (ANC)  $\geq$  1.5 K/mm^3
  - Total Bilirubin  $\leq$  2  $\times$  institutional upper limit of normal (ULN) except subjects with Gilbert's Syndrome, who must have a total bilirubin less than 3.0 mg/dL
  - Aspartate aminotransferase (AST, SGOT)  $\leq$  2.5 $\times$  institutional ULN ( $\leq$  5  $\times$  institutional ULN in the presence of liver metastases).
  - Alanine aminotransferase (ALT, SGPT)  $\leq$  2.5 $\times$  institutional ULN ( $\leq$  5  $\times$  institutional ULN in the presence of liver metastases).
  - Estimated Creatinine Clearance by Cockcroft-Gault formula  $\geq$  30 mL/min
12. All subjects, including those who are surgically sterilized, must be willing to use an effective method of contraception (barrier method of birth control or abstinence) from the time informed consent is signed until 6 months after completion of protocol therapy.
13. Subjects must consent to bank whole blood, serum, plasma for future unspecified studies.
14. Patients with 'high extent or extensive stage' of metastases (per CHAARTED (E3805) study: visceral metastasis or more than 4 bone metastases including at least 1 non-axial bone metastasis or both) should be considered unsuitable candidates for docetaxel per the treating physician's clinical judgment, or should have declined docetaxel therapy.

### 3.2 Exclusion Criteria

1. Prior cytotoxic chemotherapy for metastatic prostate cancer. Prior cytotoxic chemotherapy with curative intent in the neoadjuvant or adjuvant setting is allowed but must have been completed at least 6 months prior to registration. No cytotoxic chemotherapy is allowed during protocol specified therapy.
2. Prior concomitant therapy with ketoconazole, aminoglutethimide or abiraterone acetate or enzalutamide (MDV3100) or intent to treat with the above. Concurrent megestrol for hot flashes is allowed.
3. Prior or ongoing bisphosphonate (e.g. zoledronic acid) or RANKL inhibitor (e.g. denosumab) use is NOT allowed except when used solely for osteoporosis and strictly per guidelines for that indication. Bisphosphonate or RANKL inhibitor cannot be initiated for any indication during protocol specified therapy without consent of the sponsor-investigator of the study.
4. Prior systemic radiotherapy with strontium-89, samarium-153, rhenium-186 or rhenium-188.

5. Diagnosis of aplastic anemia, pure red cell aplasia, myelodysplasia or any of the other bone marrow failure states.
6. Any neuroendocrine differentiation including small cell carcinoma on histology or cytology.
7. No prior malignancy **except** for non-melanomatous skin cancer or non-muscle invasive bladder cancer or adequately treated Stage I or II cancer (adequacy at discretion of treating investigator) from which the subject is currently in complete remission, or any other cancer from which the subject has been disease-free for at least 3 years.
8. History of or active CNS metastasis (brain, leptomeningeal or cord compression). Brain imaging studies are not required for eligibility if the subject has no neurologic signs or symptoms suggestive of brain metastasis. Subjects with neurological symptoms are recommended to undergo a head CT scan (with or without intravenous contrast) or brain MRI (with or without intravenous contrast) to exclude brain metastasis. If brain imaging studies are performed, they must be negative for CNS disease. Skull bone involvement without neurological impact by prostate cancer is allowed.
9. Treatment with any other investigational agent within 28 days prior to registration. Subjects must not be treated with any other investigational agent while on protocol specified therapy.
10. Prior hemibody external radiation. Any external radiation therapy must have been completed at least 14 days prior to registration. Any toxicity from such therapy must have recovered to  $\leq$  grade 1 per CTCAE version 4 criteria by the time of registration.
11. Clinically significant infections as judged by the site investigator. Subjects must not have been diagnosed with human immunodeficiency virus (HIV) infection, active chronic hepatitis B or C, life-threatening illness unrelated to cancer, or any serious medical or psychiatric illness that could, in the investigator's opinion, potentially interfere with participation in this study. Subjects should be tested for hepatitis B or C or HIV infection during screening only if they are considered by the investigator to be at high risk for these infections.
12. Known hypersensitivity to bicalutamide.
13. Known gastrointestinal (GI) disease or procedure that could interfere with the GI absorption or tolerance of bicalutamide, including difficulty swallowing oral medications.
14. Grade III/IV cardiac disease as defined by the New York Heart Association Criteria (i.e., subjects with cardiac disease resulting in marked limitation of physical activity or resulting in inability to carry on any physical activity without discomfort), symptomatic pulmonary embolism within 3 months, unstable angina pectoris, myocardial infarction within 6 months, or serious uncontrolled cardiac arrhythmia as determined by the treating physician.

